ED Staffing / Subject Accrual. Because it is not possible to staff the project continuously (168 hours/week), this study will use the following sampling frame that has been used successfully in our previous ED research to ensure obtaining a representative sample of Veterans presenting to the AAVA ED. Project staff in the ED will recruit patients for the study 5 days per week between the hours of 10AM to 6PM. The majority of the recruitment time will be spent in the ED between 10AM and 6PM because 65-70% of patients enter the ED during those hours. In addition, another three days/week will include a weighted sampling of recruiting between either 7AM-3PM or 3PM-11PM time period. Thus, a total of 8 shifts (8 hours each) will be staffed each week to recruit, consent, screen patients, conduct baseline assessments, and deliver brief advice. Based on our previous ED studies where we have used similar staffing schedules we expect to accrue the following numbers: 30 months of screening x ~130 patients/month approached = 3,900; it is expected that 80% (n=3,120) will agree to participate and will be screened. We conservatively expect that 15% of the screened patients will have a positive screen and will be randomized (450 randomized; 225 per group). Randomization Procedures. Stratified random assignment to conditions will be by sex and presence of an AUD (yes/no) defined as a score of 14 for men and 10 for women on the AUDIT. Randomization by sex will be used because men and women generally differ in their rates and nature of alcohol use, problems, and outcomes. Random assignment will also be stratified based on meeting criteria for past year AUD (yes/no) because of potential differences in problem severity and potential intervention response. Randomization will proceed in blocks of 10 within study cells, in order to equalize randomization over time. Follow-up staff will be blind to condition. Participants in both conditions will receive written information regarding alcohol and VHA resources and be re-contacted to complete 3-, 6-, and 12-months follow-ups.

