Using the VA criteria for hiring and training peers, we expect that there will be a range of mental health conditions that peer mentors have dealt with in their lives. We will not exclude peers because of any conditions for which they are in stable recovery. Our priority will be to hire Veterans who are in long-term recovery. Because the peer mentors will work as part of the research team and will be supervised by the PI and the research coordinator, with support from other clinician investigators, we will have close monitoring of peer staff, as well as other staff, and are prepared to address any mental health and substance use issues that arise. If a peer is experiencing relapse, they will be assisted in seeking needed care and will not work with participants until they are stable. Also, if a peer relapses, participants will be reassigned to an alternative peer (supervised via weekly group supervision and bi-monthly individual supervision).

Follow-up Methods and Assessments. At the 3-, 6- and 12-month post-randomization follow-ups, participants will be called to complete a telephone follow-up survey. Participants may have the option to meet in person if necessary. The TLFB interview during follow-ups will be audio recorded. At enrollment, study staff will obtain consent, telephone numbers, and addresses, as well as information for contacts, at least one of whom does not live with the participant, who should know their whereabouts in the next 12 months. In addition, the following procedures will be implemented: 1) reminder calls/ letters will be started one month prior to each follow-up assessment until completed; 2) incentives will be given to participants who complete follow-ups ; and 3) participants will be encouraged to call the study office with any questions, and to notify us of address/telephone changes. A review article contains more detailed information regarding the follow-up protocol that will be used.⁶¹ Using these strategies, we typically achieve 12-month follow-up rates exceeding 80% at each assessment point.^{49,62,63}

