Self-Report Healthcare Service Use. We will use the Treatment Services Review (TSR) to measure health services use, which has adequate reliability and validity.⁷⁰ We will also access VHA electronic health data, focusing on primary care; substance abuse treatment, and psychiatric treatment services (including mutual aid groups such as AA, receiving detox services, and other substance abuse care settings).

Health Care Utilization using Medical Records. In the last year of the study, a review of participants' medical records will be conducted to determine diagnoses, service use (i.e., ED visits, hospitalizations, primary and specialty care) for one year pre- and post-entry into the study. We will use these data to assess agreement with self-report service use, particularly VHA services, and seek to understand sources of discrepancy. Data will be accessed through CPRS, Corporate Data Warehouse (CDW), and the Joint Legacy Viewer (JLV).

Health Functioning. One item from the SF-12⁷¹ will assess perceived health functioning, which are accepted

Table 2: Study Measures	Instrument	When*	#Min
Primary Outcomes			
Alcohol Consumption	TLFB	B, 3,6,12	20
Secondary Outcomes			
Alcohol Consumption	AUDIT	S, 3, 6, 12	5
Alcohol Consequences	SIP	B, 3, 6, 12	5
Health Service Use	TSR/CPRS	B, 3,6, 12	10-15
Health Functioning	SF-12	S, 3,6,12	
Depressive Symptoms	PHQ-9	B, 3,6,12	
PTSD Symptoms	PC-PTSD-5	B, 3,6,12	
Substance Use	ASSIST	B, 3, 6, 12	
Opioid Misuse	COMM	B, 3, 6, 12	
Problem Severity	BAM	B, 3,6,12	
Individual Factors			
Demographics	SAOM	S/B	5-10
Motivation to Change/Readiness	Rulers	B, 3, 6, 12	
Self-Efficacy	Ruler	B, 3, 6, 12	
Social Factors			
Social Support	mMOS	B, 3, 6, 12	10
Peers Services	WAI-SR	3	
Intervention Interaction	Metric, Sentiment		0

*S=Screen; B=Baseline, 3-month, 6-month, 12-month follow-ups

Veterans.²⁹

Substance Use

Alcohol, Smoking, and Substance Involvement Screening Test (ASSIST) is a structured interview for alcohol, tobacco, cannabis, stimulants, sedatives and opioid use disorders in general medical settings. We will use a brief screening for tobacco use (ASSIST-LITE) and the full ASSIST version 3 to measure use of all other substances.

Opioid Misuse: a modified version of the Current Opioid Misuse Measure (COMM) will assess extent of opioid medication misuse.

Individual Factors

Demographics: Background characteristics assessed include: age, sex, marital status, education, employment, income, legal history, deployment history, etc.⁷⁷

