parameter estimates that account for missing data under the missing-at-random assumption.⁸⁹ We will look for non-random attrition, and if we find, for example, attrition rates to depend on a baseline covariate, we will include this covariate in the model. If we find attrition to depend on treatment use or ideation at prior assessments, we will utilize an appropriate pattern mixture model or multiply impute data based on an appropriate pattern mixture model assumptions based on the observed missing data pattern.⁸⁸

Aim 1: Determine the efficacy of the ED APM intervention compared to BA on TLFB drinking frequency reports at 3-, 6-, and 12-months post-baseline. **Hypothesis:** Veterans with hazardous drinking who are randomly assigned to APM will have significantly greater reductions in total TLFB drinking frequency reports, compared to those assigned to CBA.

Data Analysis for Aim 1: The primary purpose of Aim 1 is to examine the impact of the intervention on frequency of drinking per TLFB interview. This outcome will likely follow the assumptions required for linear regression model, but we will adjust the model type as needed. Assuming this is the case; we will use a linear mixed-effects model and estimate the treatment effect as the difference in the time-averaged TLFB frequencies over the year of follow-up. Because reduction in problem alcohol use is of primary interest, the analysis will model change-scores from baseline in the response variable as dependent variable, and the independent variables will include the baseline values of the response variable, time in months since randomization, and the treatment group indicator. The parameter estimate of the treatment group indicator will estimate the time-averaged treatment effect. *In a second model, we will include an interaction of time by treatment group indicator to formally test the possibility that the effect varies over time. Models will include a random effect for which specific peer/clinician a participant was assigned.*

Aim 2: Determine the impact of the APM intervention on linkage to primary and specialty alcohol treatment services care, mental health symptoms and functioning at 3-, 6-, and 12-months post-baseline, compared to BA. **Hypothesis:** Veterans with hazardous drinking who are randomly assigned to APM will be significantly more likely to engage in primary, specialty care, and other VHA supportive services and to have improvements in mental health symptoms and functioning.

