Data Analysis for Aim 2: The focus of Aim 2 is to study intervention effects on secondary outcome of frequency of primary care and mental health specialty care visits (as two separate outcomes) from the TSR, calculated as an average number of visits per month during each follow-up period. Similar to Aim 1, analyses will generally use a mixed effect model framework. As described above, initial analyses will examine the distribution of outcome measures over follow-up in order to select an appropriate model (e.g. Poisson regression or a related method for counts of visits). Our analysis strategy will parallel Aim 1 in terms of the independent variables, *random effect for peer/brief advice, focus on time-average treatment effects, and additional modeling of interactions of group and time.*

Secondary Aim will determine the mediators (e.g., motivation to change, self-efficacy, coping, social support) of the effect of the intervention and linkage on subsequent alcohol use and alcohol-related consequences. **Hypothesis:** The effect of randomization to APM compared to BA on the primary outcomes (i.e., alcohol consumption and consequences) will be mediated by differences between groups in motivation to change, self-efficacy, and perceived helpfulness of peer support.

Data Analysis for Secondary Aim: *In order to establish temporal ordering, we will examine whether level of the hypothesized mediators at 3 and 6 months post-baseline mediates the effect of random assignment on 6- and 12-month measures of the three primary outcomes of alcohol use behaviors.^{90,91} We will first determine the whether study condition is associated with the hypothesized mediators over the first six months of follow-up and check for a direct effect of the mediators at 3 and 6 months on alcohol use as measured at 6- and 12-months follow-up. We will estimate the indirect effect of the intervention on alcohol use through the mediators and conduct significance testing of this effect using macros created by Preacher and Hayes.⁹²*

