Data Analysis for Exploratory Aim: Interviews will be audiotaped and transcribed verbatim for content. We will conduct analyses. We will use a rapid data analysis process, a technique used when there is a need for targeted, actionable information.⁹³ The research team will read early transcripts independently, and, in an iterative process, meet to develop and refine the coding scheme and code definitions, including developing new codes from the data based on ongoing data analysis. We will document code definitions, data interpretation, and analytic decisions in memos. Once the research team has agreed on codes and code definitions, Drs. [name] and [name], and the research supervisor, will independently review and code transcripts, meeting regularly to compare coding results, and resolving discrepancies through a consensus process. If coding definitions are refined during this process, the coders will recode transcripts already coded. Once data are coded, we will use QSR NVivo 10 software to organize the data. The study team will meet regularly to discuss code summaries and memos, developing findings with a focus on barriers and facilitators to implementation and potential testable implementation strategies. Members of the study team have used similar methods in a study of the acceptability of peer support interventions in Michigan NG soldiers.^{94,95}

Power and Sample Size Calculations

Of 450 participants randomized, we expect that at least 80% of participants will be retained (n=360). We conservatively have estimated power without accounting for methods that will allow inclusion of participants with partial follow-up data because this benefit will be off-set to an unknown degree by the additional parameters estimated in a mixed effects model. All power analyses used G*Power 3.1.9 software and a two-sided $\alpha = .05$. We calculated power based on several potential outcome measure distributions. If a linear model is appropriate, which we expect to be the case for the primary outcome of total AUDIT scores, we achieve 80% power to detect an effect size (Cohen's d) of 0.30. This is a relatively modest and reasonable effect size for studies of SBIRT models of alcohol brief interventions. For an outcome with a count distribution and assuming a mean level in controls of 1 (e.g., an average of 1 alcohol-related treatment visit in a follow-up period), we achieve 80% power to detect an incidence rate ratio of 0.75 or 1.34 under a Poisson framework.

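### Aim 2 visit outcomes come from self-report alone, while planned VHA records of the same kinds of visits serve only as an agreement check

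*Combined protocol and SAP*

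**What the plan says.** All places are in the combined protocol and SAP.

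- **Outcome source.** Data Analysis for Aim 2 names "frequency of primary care and mental health specialty care visits (as two separate outcomes) from the TSR", averaged per month within each follow-up period. The Measures section introduces the TSR under its heading for self-reported service use. Follow-up Methods and Assessments collects it by telephone, or in person if necessary.
- **Hypothesis.** Participants assigned to APM are expected to be "significantly more likely to engage in primary, specialty care, and other VHA supportive services".
- **Records.** Health Care Utilization using Medical Records plans a review of CPRS, CDW and JLV in the last study year. It covers primary and specialty care, ED visits and hospitalisations for one year either side of entry. Its stated purpose is: "We will use these data to assess agreement with self-report service use, particularly VHA services, and seek to understand sources of discrepancy".
- **Other mentions of records.** The TSR paragraph says VHA electronic data will also be accessed. Table 2 lists TSR/CPRS for health service use. Sources of Research Material says records supplement self-report. None of the three gives a rule for combining the sources.
- **Attrition.** The Missing data section relies on a mixed-effects model under missing at random. If attrition is found to depend on treatment use at prior assessments, it moves to a pattern-mixture model or to imputation on that basis.
- **Retention.** Power and Sample Size Calculations states: "Of 450 participants randomized, we expect that at least 80% of participants will be retained (n=360").

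**The concern.** Once a participant stops answering, the Aim 2 visit counts for the remaining periods are missing. VHA visits in those same months would be in an extract that the study plans to make anyway.

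Non-response may well be related to the outcome. The protocol enrols homeless Veterans who may have no telephone, and elsewhere it describes homeless Veterans as cut off from care. The people hardest to reach by telephone may therefore also differ in service use. In addition, participants know whether they had peer sessions that encouraged linkage. Only follow-up staff are described as blind, so self-reported linkage is open to differential reporting.

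At stake is whether the linkage comparison covers everyone randomised, as the intent-to-treat commitment implies, or depends on untestable assumptions about those who stopped responding. Some precision is also lost.

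**Working it through.** **Inputs**
- "450 randomized; 225 per group" (ED Staffing / Subject Accrual).
- Retention of at least 80%, n = 360 (Power and Sample Size Calculations). Follow-up Methods and Assessments adds: "we typically achieve 12-month follow-up rates exceeding 80% at each assessment point".
- "All power analyses used G*Power 3.1.9 software and a two-sided" alpha of 0.05. For a linear outcome, "we achieve 80% power to detect an effect size (Cohen's d) of 0.30". For counts, a control mean of 1 and 80% power at a rate ratio of 0.75 or 1.34.

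**Step 1: reproduce the plan's figures**
- 450 × 0.80 = 360, which is 180 per arm. 450 − 360 = 90.
- Linear: Φ(0.30 × √(180/2) − 1.96) = Φ(0.886) = 81.2% (81.0% with the t distribution). This agrees.
- Count, null variance at the control mean: Φ{[ln 1.34 − 1.96 × √(2/180)] / √(1/180 + 1/(1.34 × 180))} = Φ{(0.2927 − 0.2066)/0.0985} = Φ(0.874) = 80.9%. This agrees. A Wald version gives 84.4%.
- The lower ratio of 0.75 gives only 71% to 76% at a control mean of 1. It is close to 1/1.34 = 0.746. This does not affect the present point, because the hypothesis is for more visits.

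**Step 2: who lacks TSR data**
- The power section contrasts the 360 with participants who have partial follow-up, so 360 is best read as complete cases. On that reading, up to 90 lack some or all follow-up TSR data.
- The documents give no missingness pattern. Suppose instead that 20% miss each of the three waves (assumption), so that the ceiling of 90 applies per wave. If misses were independent, 450 × 0.2³ = 3.6, about 4 people, would have no follow-up TSR at all, and 450 × (1 − 0.8³) ≈ 220 would miss at least one wave. If the same people missed every wave, both numbers would be 90.
- The number with no follow-up TSR is therefore about 4 to 90 under these two patterns.

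**Step 3: precision if records supplied all 450**
- Standard error ratio: √(360/450) = 0.894, a reduction of about 11%.
- Detectable ratio: √(450/360) = 1.118, and exp(ln 1.34 / 1.118) = 1.30.
- Power at 1.34 with 225 per arm: 89.0% by the Step 1 formula (Wald: 91.3%).
- These powers assume Poisson variance. If the variance were twice the mean (assumption), Wald power at 1.34 would be 55.6% with 180 per arm and 65.1% with 225.

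**Step 4: possible bias (illustration only)**
- Take no true effect and an overall mean of 1 in each arm. If a fraction d is lost and the lost visit at r times the completers' rate, the completers' mean is 1/(1 − d + d × r).
- With 25% lost in BA, 15% in APM and r = 0.5: (1/0.925)/(1/0.875) = 0.95. With r = 2: (1/1.15)/(1/1.25) = 1.09.
- With the losses reversed: 1.06 and 0.92. With equal loss and equal r: 1.00.
- These are raw completer ratios. They ignore baseline adjustment and partial data.

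**Step 5: can the extract cover a full year?**
- Human Subjects Involvement and Characteristics has screening to month 12 of year 3 (study month 36) and follow-up to month 12 of year 4 (month 48). The Timeline ends follow-up in month 9 of year 4 (month 45).
- Someone enrolled in month 36 reaches 12 months at 36 + 12 = 48. An extract closed at month 45 would hold only 9 months for that person.

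**The case against.** **Records are not excluded.** Table 2, the TSR paragraph and Sources of Research Material all mention them. This stands in part: those passages leave the source of the outcome unclear. But the analysis text names the TSR alone, and no rule lets a record supply a missing count.

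**The model handles attrition.** It keeps partial responders, and there is a fallback if attrition depends on earlier treatment use. This also stands in part. Both work from assessments already made. Neither observes a visit after the last completed call, and for someone who misses every follow-up only baseline is available.

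**Records miss community care.** Both arms receive information on community resources. If peers steer people towards non-VHA services, a VHA-only count could itself be incomplete to a different degree in each arm. This stands, and it is why the TSR analysis must stay.

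**Stronger readings that the documents do not support**
- *About 90 participants will have no linkage outcome.* Retention is put at a minimum of 80%, and many non-completers may have 3- or 6-month data that the model uses.
- *The records are already being collected.* The review is planned for the last study year.
- *A fifth of the information is thrown away.* The comparison with 360 complete cases ignores partial data, which the power section says it left out.
- *A false ratio of 1.13 to 1.19 should be expected.* With 20% lost, (1 − 0.2 × 0.5)/0.8 = 1.13 and (1 − 0.2 × 0.25)/0.8 = 1.19. These require every lost APM participant to have no data and to average 0.5 or 0.25 visits, while BA loss is entirely random.

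**Conclusion.** The point holds as a worthwhile and inexpensive improvement to a secondary outcome. Aim 1 is unaffected. The plan defines Aim 2 visits from self-report, plans VHA records of the same kinds of visits over the same 12 months, and gives those records no stated role in the outcome.

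On the complete-case reading of the 360, up to 90 of 450 would lack some or all follow-up TSR data. The precision gain from using records is at most about 11% in the standard error, or a detectable ratio of about 1.30 instead of 1.34. That assumes a baseline of 360 complete cases, Poisson variance and records obtainable for everyone. The true gain is smaller to the extent that the mixed model already uses partial data.

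The size and direction of any bias cannot be determined from the documents. The main benefit is less reliance on missing at random and on reports from participants who know their assignment.

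**What to change.** 1. In Data Analysis for Aim 2, make VHA-recorded primary care and mental health specialty visits in months 0–3, 3–6 and 6–12 from randomisation the main visit outcomes. Include all randomised participants whether or not they completed calls, except those who withdraw permission for record use.
2. Keep the TSR analysis alongside, to capture non-VHA care and to check whether an arm difference in community care would change the conclusion.
3. Use the recorded visits as auxiliary information when handling TSR non-response.
4. Align Table 2, the medical-records paragraph and Sources of Research Material with this definition.
5. Reconcile the two follow-up end dates (month 9 versus month 12 of year 4), and time the extract so that it covers a full year for the last participant enrolled.

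The cost is SAP wording and some programming on an extract already planned. Its timing may need to move to the end of the study. The downside is that records miss non-VHA visits, which the retained TSR analysis only partly offsets.

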In this regard, evidence-based approaches, such as strengths-based care management, could be added to BIs to enhance efficacy; however, to be feasible in the ED and VHA, service delivery needs to be modified to minimize demands on VHA providers. Peers are ideal candidates for providing alcohol BIs and post-ED strengths-based assistance in the form of peer mentoring because of their shared experiences with patients. Peers can serve as role models and provide emotional support resulting in greater self-efficacy, healthy behavior change, and linkage to needed services.^{9,10} *Therefore, the objective of this proposed study is to conduct a hybrid randomized controlled trial (RCT) to determine the efficacy of an peer-delivered alcohol intervention starting in the ED with peer-delivered brief alcohol advice, combined with a continuing 6-session program of post-ED strengths-based peer mentorship, compared to standardized brief advice in the ED only, to facilitate reduction in risky drinking and linkage and engagement in primary and/or specialty alcohol treatment services care, if needed – an **Alcohol Peer-Mentor Intervention (APM; n=225)**, compared to **Brief Advice in the ED only (BA; n=225)** condition. The primary specific aims are to:*

Aim 1: Determine the efficacy of the ED APM intervention compared to BA on subsequent TLFB drinking frequency reports, including number of drinking days per month, number of drinks per drinking day, and number of binge drinking days at 3-, 6-, and 12-months post-baseline. **Hypothesis:** Veterans with hazardous drinking who are randomly assigned to APM will have significantly greater reductions in alcohol use as measured by TLFB reports, compared to those assigned to BA at 3-, 6-, and 12-month follow-ups.

Aim 2: Determine the impact of the APM intervention on linkage to primary and specialty alcohol treatment services care, mental health symptoms and functioning at 3-, 6-, and 12-months post-baseline. **Hypothesis:** Veterans with hazardous drinking who are randomly assigned to APM will be significantly more likely to link and engage in primary, specialty care, and other VHA supportive services and to have improvements in mental health symptoms and functioning.

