Finally, because many hazardous/harmful drinkers require linkage to services, in prior work in the ED among adults with substance use disorders, warm referral to a multi-session, in-person case management intervention increased treatment assessment ($OR=1.79$, $p<.001$) and engagement ($OR = 1.48$ $p<.05$)⁴² however, only 50% attendance with the therapist-delivered case management underscores barriers to referrals that could be more directly addressed by peers who have credibility as well as training in service options, leading us toward the peer approach proposed in this application. **Thus, our team has prior experience screening for alcohol in the ED, and delivery of interventions, with exceptional retention with longitudinal follow-up.**

Peer Support Interventions. Peer outreach programs have had wide acceptance in the VHA and numerous "grass roots" peer programs have been implemented within the VHA, and more generally in the military and National Guard (NG).⁵³ One of the leading peer outreach and linkage to mental health or other community resources in the NG is the Buddy-to-Buddy (B2B) Volunteer Veteran program implemented in the Michigan NG. Co-I Dr. **[name]** and others conducted a qualitative study of the role of peer support and linkage to treatment among Michigan NG soldiers which informed the development of the B2B program. In this program, Volunteer Veterans from the community who are outside the NG chain of command are trained in communication skills, attend drill weekends, are available by telephone to offer support and linkage to a variety of community, VA, and NG/military resources. Papers describing the partnership and development of B2B have

been published.⁵⁴ Peer support efforts, such as B2B, provide key potential resources to increase the impact of Screening, Brief Intervention and Referral to Treatment (SBIRT) but have not been used for alcohol misuse.

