Data Management. The project's data manager will conduct all data management and analysis activities under the supervision of Drs. [name] and [name]. Research staff will use double entry procedures and reconcile discrepancies. Data cleaning will be conducted throughout data collection to ensure a quality final dataset for analysis. Statistical Analysis System (SAS) will be used to examine and prepare data for the analysis.

General analytic approach. Hypotheses will be planned a priori, and will be limited to the examination of a limited number of outcomes. We will utilize an "intent-to-treat" approach. All analyses will use two-sided tests because it is possible that the APM participants might have worse outcomes compared to CBA participants. Analyses will begin with descriptive data analyses to determine distributions of key variables, to collapse categories, if necessary, and to review data for outliers and clear anomalies. Tests for linearity, independence, missingness, and distributional assumptions will also be performed. Normalizing transformations of the dependent variables will be utilized, if necessary. We will validate the randomization scheme by comparing the initial groups on key variables that could be associated with the outcomes. Where we identify significant differences between groups, we will adjust for these variables, as well as other addictions treatment received if it was not initiated by referral from the APM or CBA clinician (and thus a potential mediator of effect). Prior to fitting any analytic models, a graphical exploration of the outcome variables will be conducted to select the appropriate models based on variable distributions.

Missing data. Every effort will be made to minimize missing data. Where we have missing covariates that are necessary for analysis, we will perform multiple imputation of missing data and combine the results from 5 imputations based on Rubin's method to produce an estimate and the corresponding confidence interval accounting for missing data uncertainty.⁸⁸ For follow-up attrition, the proposed mixed-effects regression model will allow the use of data from all participants (not just those with complete follow-up) and provide unbiased

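### Aim 2 asks whether more Veterans link to primary and specialty alcohol care, but the only service-use outcome analysed is mean visits per month to primary care and mental health care

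*Combined protocol and SAP*

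**What the plan says.** Aim 2 is worded in both Specific Aims and Data analyses as "Determine the impact of the APM intervention on linkage to primary and specialty alcohol treatment services care". The hypothesis in Specific Aims is that APM Veterans "will be significantly more likely to link and engage in primary, specialty care, and other VHA supportive services". Data analyses restates it as "will be significantly more likely to engage in primary, specialty care, and other VHA supportive services", so the verb for linking drops out of the hypothesis while the aim sentence above it still refers to linkage.

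Data Analysis for Aim 2 names the "secondary outcome of frequency of primary care and mental health specialty care visits (as two separate outcomes) from the TSR". The metric given for both of these is a monthly rate, "calculated as an average number of visits per month during each follow-up period". The model is a mixed-effects one, with a Poisson or similar count model chosen after the distribution has been inspected. The independent variables follow Aim 1, whose list includes the baseline value of the response. The General analytic approach adds an outlier review and says "Normalizing transformations of the dependent variables will be utilized, if necessary".

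No section defines linkage, names a yes/no linkage outcome, gives an expected proportion linked, or powers one. The Preliminary Studies section reports the team's earlier linkage results on a yes/no scale: "warm referral to a multi-session, in-person case management intervention increased treatment assessment" (OR 1.79), with OR 1.48 for engagement.

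**The concern.** The hypothesis is about persons: are more of them linked? The outcome is a rate of visits. A mean rate combines how many people make contact with how often those in contact attend, and the plan has no step that separates the two.

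This matters because Veterans already in primary care or mental health care may enrol. Only recent substance abuse treatment and recent peer services are excluded, and the Background section expects some participants to be VHA service users already. Added visits by such patients could be reported as better linkage, and a real rise in first contacts could be lost in the spread of the counts.

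The service types do not match either. The aim names specialty alcohol treatment, the outcome counts mental health specialty visits, and the example in Power and Sample Size Calculations is an alcohol-related treatment visit. The Secondary Aim also refers to the effect of linkage on later drinking, and no linkage variable is defined there.

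**Working it through.** **Inputs from the documents.** 450 randomised 1:1 and 80% retained, so 450 × 0.80 / 2 = 180 per arm; two-sided alpha 0.05; control mean of 1 visit per follow-up period; OR 1.79 and 1.48 from earlier work. **Not in the documents, so assumed:** control linkage, visits per linked person, and skew.

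**1. The plan's own figure.** Poisson rate ratio, with null variance at the base rate:

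power = Φ{[ln 1.34 − 1.96√(2/180)] / √[(1 + 1/1.34)/180]} = Φ{(0.2927 − 0.2066)/0.0985} = Φ(0.874) = 80.9%.

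The stated 80% for a rate ratio of 1.34 is reproduced (the Wald form gives 84.4%). The stated 0.75 gives only 71-76%, but it is not the hypothesised direction. These figures assume plain Poisson variation. With negative binomial dispersion k, the Wald variance is [(1 + k) + (1/1.34 + k)]/180, and power falls to 53% at k = 1 and 37% at k = 2.

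**2. When a mean tracks linkage.** With homogeneous Poisson visits, P(any visit) = 1 − exp(−mean). A mean of 1 gives 63% and a mean of 1.34 gives 74%, so mean and share linked move together. They separate only with skew or excess zeros.

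**3. How they can separate.** One weekly attender over a 6-month period makes about 26 visits. In an arm of 180 that moves the mean by 26/180 = 0.14 visits, the same as 26 people (14% of the arm) each linking once. If that person attended weekly before enrolment, baseline adjustment largely removes this; if the attendance is new, it does not.

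Assumed mixture: 30% of controls link; 14% of linkers average 15 visits and the rest 1.5. Control mean = 0.30 × (0.14 × 15 + 0.86 × 1.5) = 1.02.

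- *Missed linkage.* Linkage rises to 45%, the added linkers being light users. The heavy share of linkers becomes 0.14 × 0.30/0.45 = 9.3%, and the mean 0.45 × (0.093 × 15 + 0.907 × 1.5) = 1.24. In simulation (4,000 trials), a robust test of means rejects in 12% of trials and a yes/no test in 84%.
- *Apparent linkage.* Linkage stays at 30% and the heavy share doubles to 28%. The mean is 0.30 × (0.28 × 15 + 0.72 × 1.5) = 1.58. The robust test of means rejects in 32% and the yes/no test in 5%. An unadjusted Poisson test rejects in 83%, but it also rejects in 53% when the arms are identical, so much of that figure is a variance failure.

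**4. Power of a yes/no outcome.** Treatment odds = OR × p0/(1 − p0), and

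power = Φ{[(p1 − p0) − 1.96√(2p̄(1 − p̄)/180)] / √[(p0(1 − p0) + p1(1 − p1))/180]}.

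For p0 = 0.30 and OR 1.79, p1 = 0.434 and power = Φ{(0.1341 − 0.0996)/0.0503} = 75%.

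| Assumed control linkage | APM at OR 1.79 | Power |
|---|---|---|
| 15% | 24% | 58% |
| 20% | 31% | 66% |
| 30% | 43% | 75% |
| 80% | 88% | 51% |
| 90% | 94% | 31% |

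At OR 1.48, with control linkage of 10-50%, power is 22-45%.

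**5. Illustrative comparison.** Assumptions: OR 1.79; control linkage 15-30%; visits per linked person = 1 + negative binomial with mean 3 and dispersion 0.5 to 2; one time point; no baseline adjustment.

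| Analysis | Power |
|---|---|
| Any visit, yes/no | 57-77% |
| Raw mean visits, Welch test | 29-51% |
| Log(1 + visits) | 48-67% |
| Raw mean visits, if APM also raises visits per linked person from 4 to 6 | 65-99% |

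**The case against.** The defence has four good points.

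- **Engagement is half of the hypothesis.** Visit frequency is a reasonable measure of it, so the outcome should stay. A reader might infer that mean visits have no bearing on Aim 2; the text does not support that.
- **Existing use is partly handled.** Aim 2 carries over Aim 1's adjustment for the baseline value, and the Treatment Services Review (TSR) is collected at baseline. Stable prior use is therefore not simply counted as linkage. What remains is that an increase by an existing user and a first contact by a new one enter the outcome in the same way.
- **Skew is not established.** A reader might infer that a few heavy users do dominate the mean. The documents give no visit distribution, so the most that can be said is that they could. Outlier review, transformation and a data-led choice of count model are partial safeguards. A hurdle model would separate contact from frequency, but none is prespecified.
- **The power gap is not a property of the plan.** The comparison in step 5 gives the yes/no test an advantage, because visits per linked person are set equal in the two arms. It omits the planned repeated measures and baseline adjustment. It also borrows an odds ratio for treatment assessment in adults with substance use disorders. Allowing the log transformation narrows the gap, and adding an effect on visits per linked person reverses it.

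None of this supplies an estimate of the share linked, or brings alcohol treatment into the analysis.

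**Conclusion.** The concern holds as a mismatch between question and outcome. As written, the plan gives no estimate of the proportion of Veterans linked in either arm and no analysis of linkage to specialty alcohol treatment, although Aim 2 names both primary care and specialty alcohol treatment. This follows from the text and needs no assumption.

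The statistical consequence is conditional. Mean visits can miss or imitate a change in linkage if visits are skewed or have many zeros, and baseline adjustment lessens the problem without removing it. The power ranges above are illustrative: they rest on assumed control linkage, assumed skew and, for the unfavourable comparison, no change in visits per linked person. They do not show that the yes/no outcome is generally more powerful. The reason to add it is that it answers the question asked. The primary drinking outcome is not affected.

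**What to change.** In Data Analysis for Aim 2:

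- **Add a yes/no linkage outcome:** at least one visit of the given type after randomisation, by 3, 6 and 12 months.
- **Name the service types:** primary care, specialty alcohol or substance use treatment, and mental health specialty care if still wanted.
- **Model:** mixed-effects logistic regression, adjusted for any visit of that type at baseline. Because the indicators are cumulative within a person, include a participant random effect beside the planned one for peer or brief advice. For substance use treatment, the 3-month exclusion will leave a baseline term over that window nearly constant, so the plan should say it may be dropped.
- **First contact:** report those with no baseline visit of that type descriptively, by arm.
- **Engagement:** keep visits per month, labelled as such.
- **Power statements:** label any comparison of the two outcomes as illustrative and list its assumptions.

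Cost: SAP wording and a few more secondary estimates, to be weighed against the plan's intention to limit the number of outcomes. No new data are needed, since the TSR and VHA records already cover primary care, substance abuse treatment and psychiatric care. Power will be low for primary care if most controls attend anyway: at OR 1.79, about 51% with 80% control contact and 31% with 90%, both control rates being assumed.
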